5.3 Screen failures

A screen failure occurs when a participant who consents to participate in the clinical study is subsequently found to be ineligible and therefore will not receive the study treatment. A minimal set of screen failure information is required to ensure transparent reporting of screen failure participants to meet the Consolidated Standards of Reporting Trials (CONSORT) publishing requirements and to respond to queries from regulatory authorities. Minimal information includes demography, screen failure details, eligibility criteria, and any serious adverse event (SAE).

5.3.1 Participant numbering

Each participant is identified in the study by a Participant Number (Participant No.), that is assigned when the participant is enrolled for screening and is retained for the participant throughout his/her participation in the trial. The participant number will be different to the core study participant number. The Participant No. consists of the Site Number (Site No.) (as assigned by Novartis to the investigative site) with a sequential participant number suffixed to it, so that each participant's participation is numbered uniquely across the entire database. Upon signing the informed consent form, the participant is assigned to the next sequential Participant No. available. In order to link between the core study and the extension study, the participants No. of the core study will be recorded in the respective CRF in the extension study.

6 Study treatment(s) and concomitant therapy

6.1 Study treatment(s)

During the extension study, participants will be receiving the same dose of ligelizumab as assigned at randomization in the core studies. There is a possibility to discontinue the study treatment in the MR participants who successfully continue "conditional discontinuation of study treatment" (Section 4.1.2).

Study treatment includes investigational drug ligelizumab (120 mg/ml) and placebo, all participants will receive 2 injections, so participants on 120mg/ml will also receive a matching placebo injection to protect the study blinding. Study treatment must be administered by an independent drug administrator or unblinded pharmacist at the study site who is not involved in any of the study assessments. The procedure for the administration at home is summarized in the Section 6.2.3.1. The administration will be performed by the participant and/or parent/caregiver in the case of a child/adolescent at home.

Novartis will supply ligelizumab (QGE031) 120 mg per 1 mL as prefilled syringe (PFS) preassembled within a needle safety device (NSD) from the Becton Dickinson UltraSafe PassiveTM NSD X100L Plus series and placebo.

Table 6-1 Investigational and control drug

Investigational/ Control Drug (Name and Strength)	Treatment Form or Pharmaceutical Dosage Form	Route of Administration	Presentation	Sponsor (global or local)
QGE031 120mg/1ml	Solution for injection	SC	Double-blind	Sponsor (global)
QGE031 Placebo/1ml*	Solution for injection	SC	Double Blind	Sponsor (global)

^{*} Placebo will only be administered alongside the 120mg/1ml dose to protect the dose blinding. There is no placebo arm

6.1.1 Bio-batch retention samples

Not applicable.

6.1.2 Additional study treatments

No other treatment beyond investigational drug and control drug are included in this trial.

6.1.3 Treatment arms/group

Participants will be assigned to one of the following two treatment arms depending on responder status in the previous study/ies) as per Section 4.1.1 and Section 4.1.2.

Each participant (except the MR participants undergoing conditional discontinuation) will receive two (2) SC injections every four weeks starting at Day 1.

- 1. ligelizumab 240 mg arm: 2 injections of 1.0 mL ligelizumab
- 2. ligelizumab 120 mg arm: 1 injection of 1.0 mL ligelizumab and 1 injection of 1.0 mL placebo

The assignment to receive 120 mg or 240 mg ligelizumab will be determined by treatment received during the previous study(ies). All participants (except the MR participants undergoing conditional discontinuation (Section 4.1.2)) will receive study drug (ligelizumab). There is no placebo arm.

Of note, based on CQGE031G12301 core study results, Novartis will assess the need to switch participants in CQGE031G12303B to a different dose than the one they were receiving in CQGE031G12301.

6.1.4 Treatment duration

The planned duration of treatment is up to 156 weeks (three years). There is a possibility of a shorter treatment period than three years in the MR participants who successfully continue "conditional discontinuation of study treatment" (Section 4.1.2).

6.1.5 Medical devices

Not applicable.

6.2 Preparation, handling, storage, and accountability

Each study site will be supplied with study treatment in packaging as described under Table 6-1 Investigational and control drugs section.

A unique medication number is printed on the study medication label.

An independent unblinded administrator will identify the study treatment kits to dispense to the participant by contacting the Interactive Response Technology (IRT) and obtaining the medication number(s). The study treatment has a 2-part label (base plus peel-off label). Immediately before preparing study treatment, the unblinded pharmacist (or authorized delegate) will detach the outer part of the label from the packaging and affix it to the source document.

The guidelines for the storage, preparation and administration of study treatment are described in the pharmacy manual (provided separately).

As per Section 4.5, during a public health emergency as declared by local or regional authorities i.e., pandemic, epidemic or natural disaster, that limits or prevents on-site study visits, delivery of IMP directly to a participant's home may be permitted for the participants or parents/caregivers who have completed the training of injection (if allowed by local or regional health authorities and ethics committees, as appropriate) or in the event the Investigator has decided that an on-site visit by the participant is no longer appropriate or possible. The dispatch of IMP from the site to the participant's home remains under the accountability of the Investigator. Each shipment/provisioning will be for either 12 or 16 weeks as per IRT supply. In this case, regular phone calls or virtual contacts (every 4 weeks or more frequently if needed) will occur between the site and the participant for instructional purposes, safety monitoring, investigation of any adverse events, ensuring participant continues to benefit from treatment, and discussion of the participant's health status until the participant can resume visits at the study site.

6.2.1 Handling of study treatment

Study treatment must be received by a designated person at the study site, handled and stored safely and properly and kept in a secured location to which only the Investigator and designated site personnel have access. Upon receipt, all study treatment must be stored according to the instructions specified on the labels and in the Investigator's Brochure.

Clinical supplies are to be dispensed only in accordance with the protocol. Technical complaints are to be reported to the respective Novartis Country Organization Quality Assurance.

Medication labels will be in the local language and comply with the legal requirements of each country. They will include storage conditions for the study treatment but no information about the participant except for the medication number.

The Investigator or designated site staff (blinded or unblinded, as applicable) must maintain an accurate record of the shipment and dispensing of study treatment in a drug accountability log. Monitoring of drug accountability will be performed by field monitors during site or remote monitoring visits, and at the completion of the trial. The Investigator must provide accountability also for locally sourced materials used for administration.

At the conclusion of the study, and as appropriate during the course of the study, the investigator will return all unused study treatment, packaging, drug labels, and a copy of the completed drug accountability log to the Novartis monitor or to the Novartis address provided in the investigator folder at each site. If study treatment is administered at home, participants will be asked to return all unused study treatment and packaging at the end of the study, and as appropriate during the course of the study or at the time of discontinuation of study treatment.

6.2.2 Handling of other treatment

All rescue medication regardless of dispensation method, must be documented in source and closely monitored. Participants should be reminded to bring rescue medication to all study visits. This applies to the following:

- Short-acting Beta-agonist (SABA) (for participants with a documented diagnosis of asthma)
- Epinephrine (e.g., EpiPen)

If rescue medication is provided at the study site it must be handled and stored according to the package label, kept in a secured location and dispensed only in accordance with the protocol.

The investigator must maintain an accurate record of dispensing of the above-mentioned treatment in a drug accountability log/inventory log, and source documents. Monitoring of drug accountability will be performed by monitors during site visits and at the completion of the study. Participants will be asked to return all unused SABA and epinephrine treatments and packaging at the end of the study or at the time of discontinuation from the study.

Any unused epinephrine and SABA stored at the site will be disposed of according to local regulation.

6.2.3 Instruction for prescribing and taking study treatment

The independent study treatment administrator or unblinded pharmacist will administer the study treatment to the participant during the study visit without engaging in any unnecessary interactions that may have the potential to un-blind the participant or any of the study site personnel.

The subcutaneous injections can be administered in the deltoid region on the upper right and/or left arm, the lower stomach area (but not the area 5 cm around the belly button) and/or into the front of the right and/or left thigh, or the abdomen as preferred by the participant and/or site. Do not inject into skin that is tender, bruised, red, scaly, hard or into areas with scars or stretch marks. Each injection must be administered at a different site (e.g., right arm and left thigh). The guidelines for the preparation and administration of study treatment are described in the pharmacy manual (provided separately).

Participants who join the study after the follow-up period of the core study will remain on site for observation for a period of **2 h post-dose** for the first three drug administration visits, this equates to week 0, 4 and 8. Thereafter a 30 minute wait will suffice. Participants who join the extension study from continuous treatment will only require a 30 minute wait at the site. The 2-hour observation period for the first three drug administrations must be observed in all instances where study treatment is reintroduced after a washout/interruption period (e.g., restart of the

study treatment after the conditional discontinuation of study treatment because of no longer MR).

At Week 52, 104, and 156 there must be a minimum of 1 hour between administration of study treatment and performing the OFC (Section 8.3.1). Study treatment must be given before the OFC.

In case the study treatment should be started based on the responder driven approach (Previous MR is no longer MR after off-treatment, Section 4.1.2), the time interval between OFC and restart of study treatment must be a minimum of 24 h.

These observation periods follow the recommendation suggested by the National Heart, Lung, and Blood Institute and by the American Academy of Allergy, Asthma & Immunology and the American College of Allergy, Asthma and Immunology Executive Committees Joint Task Force (Cox et al 2007) for the anti-IgE therapy currently available (omalizumab). As described in the Investigator Brochure, the site needs to ensure readiness to react to anaphylactic events (e.g., immediate availability of qualified staff, available injectable epinephrine, antihistamine, corticosteroids, intravenous supplies, oxygen, an oral airway, Ambu bag and the ability to transport a participant rapidly to an emergency department/hospital).

The dose for individual participants will be the same within a treatment arm and will be managed by the IRT.

All study treatment dosages prescribed and dispensed to the participant and all dosing errors or missed administrations during the study must be recorded on the appropriate electronic case report form (eCRF).

All kits of study treatment assigned by the IRT will be recorded in the IRT system. The investigator must promote compliance by instructing the participant to take the study treatment exactly as prescribed and by stating that compliance is necessary for the participant's safety and validity of the study. The participant must also be instructed to contact the investigator if he/she is unable, for any reason, to take the study treatment as prescribed.

6.2.3.1 Administration at home by participant or parent/caregiver

The study treatment should only be administered via PFS by adults. In other words, if the participant is below 18 years (< 18), the administration should be done by his/her parent/caregiver. Even an adult participant who is willing to be part of the administration at home **BUT** not comfortable with self administration, in this instance the parent/caregiver can be an administrator.

The participant will be given the option to start administration at home once their training is completed. The participants doing conditional discontinuation of study treatment won't be offered the opportunity of drug administration at home.

Before initiation of training visit, participants who are willing to take part in administration at home should be evaluated according to the below criteria. If the criteria are satisfied, then the Instruction For Use (IFU) Guide will be provided to the participants or caregiver who will then undergo training in administration of the study treatment.

The clinical eligibility criteria for administration at home of ligelizumab are below:

- participant/caregiver should be capable and willing to self-administer ligelizumab.
- participant/caregiver should know how to recognize symptoms/signs of severe hypersensitivity reactions

For the first and second use of PFS, the injection will take place as a site staff assisted injection i.e., with the help of the site staff performing the injection steps. At the third use of PFS, the self-injection will take place under supervision however without the help of the site staff, i.e., the site staff only observes and does not help in performing the injection steps. The training of each injection, be it assisted or under supervision, will be provided individually by the site staff to the participant/caregiver.

Participants who administered ligelizumab at home in the first year of the extension study and continue into the second/third year of the study, will continue the home-administration. However, those participants who are unable to adhere to administration at home in the first year of study can then revert to clinic visits, they will subsequently be supported by the clinic to do home administration and training during the second/third year.

First dose of PFS: Assisted administration of study treatment

- The site staff will show the participant how to use the PFS based on the instructions provided in the IFU, with emphasis on specific checks for device use evaluation.
- Participant will be given the opportunity to raise questions if any.
- Participant will perform the injection into an appropriate injection site of the body with the site staff **actively assisting** him/her during the injection. If the site staff observes that the participant is performing an action that may jeopardize the participant's safety, site staff will intervene to prevent any potential harm and guide/correct the participant.

Second dose of PFS: Assisted supervision of study treatment

- Study staff should ask the participant whether they wish to be retrained prior to injection. If needed, site staff will retrain the participant.
- Participant will perform the injection into the appropriate injection site of the body with the site staff **actively assisting** him/her during the injection. If the site staff observes that the participant is performing an action that may jeopardize the participant's safety, site staff will intervene to prevent any potential harm and guide/correct the participant.

Third dose of PFS: Supervised administration of study treatment

- Participant will perform the injection into the appropriate injection site of the body mimicking an outside of clinic administration i.e., without the active assistance of the site staff but under their supervision.
- If the site staff observes that the participant is performing an action that may jeopardize the participant's safety, site staff intervene to prevent any potential harm and guide/correct the participant.
- The site staff will observe that the dose is administered in accordance to the steps indicated in the self-injection assessment list and the potential hazard assessment list as described in the pharmacist manual. The site staff will observe the participant actions as per the lists to evaluate if the participant is capable of self-administration outside of clinic.

Thereafter, outside of clinic administrations should be done at pre-defined time points as per assessment schedule (Table 1-4). If self-administration is performed by a parent/caregiver, the parent/caregiver will then be trained as outlined above.

All participants self-administering study treatment at home should remain under observation by a family member or colleague, for symptoms and signals of hypersensitivity in a quiet environment for 30 minutes after each administration.

Participants carrying out administration outside the clinic setting will:

- have in-clinic safety and efficacy assessments done at least at Weeks 24, 52, 76, 104, 128 and 156 intervals
- on site visits will take place every 12-16 weeks, to collect study treatment (2 or 3 kits), review dosing log and safety check
- At the site visits, participant or parent/caregiver will be offered the opportunity to perform a self administration under the supervision of the study staff and to be retrained on the injection technique upon request or if whenever required.
- be assessed remotely (i.e., outside of clinic) by safety phone call from the site every 4 weeks either on the day of study treatment administration or 1 to 3 days after, unless there is an inclinic visit scheduled (at Weeks 24, 52, 76, 104, 128 and 156 as per protocol).

During outside of clinic administrations, participants are expected to contact the investigator/site staff in case they are experiencing any AE/SAEs or have any concerns immediately.

At any time during the study, should a participant or parent/caregiver or investigator decide not to continue with administration of study treatment at home, the participant must contact the site, or the site staff must contact the participant, to arrange for all subsequent visits and treatments to be administered at the site.

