• Conditional discontinuation of study treatment is only for the participants who showed maximum response by DBPCFC (EOT of the core study)/OL-OFC (the extension study). Conditional discontinuation will be allowed only once in any given participant through the entire study. After start of the interruption of study treatment, participants will be allowed to re-start treatment in case of clinical (allergic reactions to food) or other findings (e.g., SPT) suggesting of resurgence of the allergic phenotype. Following these indications, the investigator proposes an optional OL-OFC to more formally re-assess the level of reactivity of the participants and decide on reintroduction of study treatment. As the risk of

anaphylaxis related to the reintroduction of treatment after the washout period has not yet been characterized in this population, participants who will restart study treatment must remain on-site for observation for a period of 2 h post-dose for the first three drug administrations.

Study treatment administration at home:

Ligelizumab will be administered using a single-use, disposable combination product, intended for the subcutaneous (SC) application of a fixed dose of ligelizumab. The combination product consists of a pre-filled syringe (PFS) pre-assembled within a needle safety device (NSD) from the Becton Dickinson UltraSafe PassiveTM NSD X100L Plus series (hereinafter called QGE031 PFS in X100L Plus). The design and technical features of the QGE031 PFS in X100L Plus combination product are based on well-established technology and are in line with the current common treatment technology for self-injection drugs. It is permitted for adult participants to do self-administration with QGE031 PFS in X100L Plus while children and adolescent participants must be administered QGE031 PFS in X100L Plus by parent/caregiver. Parent/caregiver can also administer QGE031 PFS in X100L Plus to adult participants, if necessary.

Eligibility criteria

The participants in this basket extension study should have successfully completed a core study. Therefore, the participants who developed any condition meeting discontinuation criteria during a core study, AND/OR participants who developed any clinically significant medical condition listed in the exclusion criteria of a core study judged by the investigator, must not be rolled over into this study.

Oral food challenge (OFC)

In this extension study, open-label OFC will be conducted.

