Administration at home will be commenced in the first year of the study in the non MR participants who transition at the end of follow-up period of the core study as well as non MR participants who transition at the end of treatment period of other studies. For those participants, who started the home-administration in year 1 and continue the treatment in years 2 and 3, they will be able to continue the administration at home for the remainder of the study.

It will be possible to start the administration at home also in the second/third year for participants no longer MR at the end of first/second year or in participants who express the interest in administration at home after the first/second year of treatment.

The detailed process of administration at home is written in Section 6.2.3.

Rationale for starting points of administration at home

To allow sufficient training to participant or parent/caregiver on the use of pre-filled syringe (PFS), training will commence at Week 16 and thereafter take place at Weeks 20 and 24. The first self-administration outside the clinic could start at Week 28 of the extension treatment period. However, if the investigator feels it is in the best interest of the participant, they can defer the training until a suitable timepoint, in agreement with the site staff and participant. In addition, before start of training, the clinical data of the participants who will be administered at home should be frozen in the electronic data capture (EDC) system (confirmed by Novartis Data Management) so that the blinded data of the core study can be protected despite potential un-blinding occurring during the administration at home without "unblinded" administrator.

[figure not shown]
For participants starting the administration at home after the first/second year the training visits will be:

- **after first year:** training at weeks 56, 60 and 64 with the first administration at home on week 68
- **after second year:** training at weeks 108, 112 and 116 with the first administration at home on week 120

 Table 4-2
 Home Administration Assessment Schedule

Period	Screening- Treatment	Treat	tment																	
Visit Name	SCRN/Day 1	WK 4	WK 8	WK 12	WK 16	WK 20	WK 24	WK 28	WK 32	WK 36	WK 40	WK 44	WK 48	WK 52- OFC	WK 56	WK 60	WK 64	WK 68	WK 72	WK 76
Week	1	4	8	12	16	20	24	28	32	36	40	44	48	52	56	60	64	68	72	76
Days	1	28	56	84	112	140	168	196	224	252	280	308	336	364	392	420	448	476	504	532
Informed consent	Х																			

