Informed consent																				
Inclusion / Exclusion criteria																				
Demography/ Medical history																				
Adverse Events	Χ	Х	Х	Х	Х	Х	Х	Х	Х	Х	Х	Х	Х	Х	Χ	Х	Χ	Χ	Χ	Х
Concomitant medications, therapies, procedures	X	Х	X	X	X	Х	X	Х	X	Х	Х	X	Х	X	X	X	X	Х	X	X
Patient reported outcomes (PROs)							approx. 10 days before and 3 days after the OFC													approx. 10 days before and 3 days after the OFC
Physical Examination							S						S							S
Electrocardiogram (ECG)							Х													Х
Body Weight							Х													Х
Body Height							S													S
Vital Signs							Х						Х							Х

Period		Treat	tment	Period																
Visit Name	WK 80	WK 84	WK 88	WK 92	WK 96	WK 100	WK 104- OFC	WK 108	WK 112	WK 116	WK 120	WK 124	WK 128	WK 132	WK 136	WK140	WK 144	WK 148	WK 152	WK 156- OFC
Weeks	80	84	88	92	96	100	104	108	112	116	120	124	128	132	136	140	144	148	152	156
Days	560	588	616	644	672	700	728	756	784	812	840	868	896	924	952	980	1008	1036	1064	1092
Spirometry in co- morbid asthma only							Х													X
Urine pregnancy test ²	S	S	S	S	S	S	S	S	S	S	S	S	S	S	S	S	S	S	S	S
Serum Pregnancy test																				
Clinical Chemistry & Hematology							Х						Х							Х
Urinalysis dipstick							S													S
Stool Sample (ova & parasitic test) by local lab																				

[figure not shown]
Period		Treat	tment	Period																
Visit Name	WK 80	WK 84	WK 88	WK 92	WK 96	WK 100	WK 104- OFC	WK 108	WK 112	WK 116	WK 120	WK 124	WK 128	WK 132	WK 136	WK140	WK 144	WK 148	WK 152	WK 156- OFC
Weeks	80	84	88	92	96	100	104	108	112	116	120	124	128	132	136	140	144	148	152	156
CC	560	588	616	644	672	700	728	756	784	812	840	868	896	924	952	980	1008	1036	1064	1092
Skin Prick Test ⁴							Х						Χ							Х
Contact IRT			Χ				Х			Χ			Χ			Х				Х
Home Administration Training								X ⁵	X ⁵	X ⁵										
Study Treatment Administration (on-site)			X				X ⁶			Х			Х			X				X ⁶
Dispense Home Administration Dosing Log																				
Study Treatment Administration (at home)	X	X		X	X	X		X	X		Х	X		X	X		Х	Х	Х	
Safety Phone Call (at home)	Х	Х		Х	Х	Х		Х	Х		Х	Х		Х	Х		Х	Х	Х	
Study Treatment Accountability			S				S			S			S			S				S
Review Home Administration Dosing Log			X				Х			Х			Х			Х				X
Providing rescue medication, counseling, training & accountability			S				S			S			S			S				S

Period		Treat	tment	Period																

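### The home-dosing rule and Table 4-2 make no exception for restarts, although Sections 2.3 and 6.2.3 require on-site observation for the first three doses after an interruption

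*Protocol*

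**What the plan says.** **Observation after a restart.** Protocol Section 6.2.3 states: "The 2-hour observation period for the first three drug administrations must be observed in all instances where study treatment is reintroduced after a washout/interruption period". Its example is a restart after conditional discontinuation when the participant is no longer a Maximum Responder (MR). Section 2.3 fixes the place: "participants who will restart study treatment must remain on-site for observation for a period of 2 h post-dose for the first three drug administrations".

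**Home dosing.** Section 6.2.3.1 says that participants who dosed at home in the first year and "continue into the second/third year of the study, will continue the home-administration". Section 4.1.3 has a parallel sentence on those "who started the home-administration in year 1 and continue the treatment in years 2 and 3". Under Section 6.2.3.1, participants who self-administer at home "should remain under observation by a family member or colleague" for 30 minutes after each dose.

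**Who is kept out of home dosing.** Section 6.2.3.1 adds: "The participants doing conditional discontinuation of study treatment won't be offered the opportunity of drug administration at home". Section 4.1.3 lets participants who are no longer MR at the end of year 1 or 2 start home dosing, after training at Weeks 56, 60 and 64 or Weeks 108, 112 and 116.

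**Schedule.** Section 1.3 refers home-dosing participants to Table 4-2. In that table the row whose label begins "Study Treatment Administration (at home" sets the home doses. Footnote 5 limits the later training visits to patients who started treatment after the first or second year. No footnote deals with restarts.

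**The concern.** A participant can dose at home from Week 28, become MR at Week 52, stop drug, and restart at Week 68 or Week 104. Another can dose at home up to Week 104, become MR then, stop, and restart at Week 120. Both went on into year 2 or 3 after home dosing in year 1, so the Section 6.2.3.1 rule can be read as returning them to home dosing. Sections 2.3 and 6.2.3 require their first three doses to be observed on site. A site following one text departs from the other.

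The protocol itself treats restart as a distinct hazard. Section 2.3 says that the anaphylaxis risk on reintroduction has not been characterised in this population, and that two of the four positively adjudicated anaphylaxis cases in completed studies followed a restart of ligelizumab.

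There is also an analysis consequence. Home-administration safety is a secondary objective (SAP Section 2.6.1). If some sites give early re-exposure doses at home, the home summary mixes them with maintenance doses and nothing in the plan separates the two.

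**Working it through.** No sample size or error rate is involved. The check is to find where the doses after each restart fall in Table 4-2.

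**Inputs**
- On-site doses: Day 1 and Weeks 4, 8, 12, 16, 20, 24, 36, 52, 64, 76, 88, 104, 116, 128, 140 and 156 (17 doses).
- Home doses: Weeks 28, 32, 40, 44, 48, 56, 60, 68, 72, 80, 84, 92, 96, 100, 108, 112, 120, 124, 132, 136, 144, 148 and 152 (23 doses).
- 17 + 23 = 40, which accounts for every four-weekly dose from Day 1 to Week 156.
- Scheduled restart points for a previous home user (Section 4.1.2.1): Weeks 68, 104 and 120.

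**Check of the coding.** Section 6.2.3 says that the first three doses on entry are at Weeks 0, 4 and 8. All three come out on site, as they should.

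**Doses 2 and 3 after a restart at week w fall at w + 4 and w + 8**

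| Restart | Dose 2 | Dose 3 |
|---|---|---|
| Week 68 | Week 72: home | Week 76: on site |
| Week 104 | Week 108: home, also marked as training | Week 112: home, also marked as training |
| Week 120 | Week 124: home | Week 128: on site |

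Dose 1 is left out of the count. It must follow the challenge by at least 24 hours, and Table 4-2 does not place such a dose. It marks Weeks 68 and 120 themselves as home doses.

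**General property of the table.** After Week 24 the gaps between successive on-site doses are 12, 16, 12, 12, 12, 16, 12, 12, 12 and 16 weeks. The smallest is 12 weeks and doses are 4 weeks apart, so no two consecutive doses after Week 24 are both on site. Leaving the training row aside, at least one of doses 2 and 3 is a home dose whatever the restart week, including a restart after an ad hoc challenge.

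**Training visits.** Under Section 4.1.3, training at Weeks 108, 112 and 116 would keep doses 2 and 3 of a Week 104 restart on site. That section ties training to starting home dosing late, while footnote 5 ties it to starting treatment late. Neither says whether a participant trained in year 1 and restarted at Week 104 is included. For Week 68 and Week 120 restarts, no training visit falls at Week 72 or Week 124.

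**Not affected.** A participant off drug since Day 1 who restarts at Week 52 has no year-1 home dosing to continue. If that participant takes up home dosing, training at Weeks 56 and 60 keeps doses 2 and 3 on site.

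**The case against.** The strongest reply is that Section 6.2.3 already governs. It is mandatory, covers all reintroductions and names this very case, whereas the home rule is general and never mentions restarts. On that reading only a cross-reference is missing. Much of this stands:

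- A reader might infer that the protocol assigns restart doses to the home. It does not. The result comes from applying the home rule and Table 4-2 to restarters.
- Section 4.1.3 is narrower than Section 6.2.3.1. A participant interrupted as MR has arguably not continued the treatment.
- A reader might count two of the three doses after a Week 104 restart as home doses. The text does not support a firm count, because the training visits may apply.
- A reader might extend the point to every home user who restarts. The continuing rule in Section 6.2.3.1 names only those who dosed at home in year 1.
- Table 4-2 has no food challenge at Week 68 or 120, so it may not have been drawn with restarters in mind.
- The IRT controls restarts (Sections 4.1.2 and 6.3.1), and the investigator can return a participant to on-site dosing at any time.
- Protocol Section 9.3.2 already plans separate safety tables for participants who restart after a mandated interruption of more than 16 weeks.

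This does not dispose of the point. No text gives Section 6.2.3 precedence over a rule that says home dosing will continue. The bar on home dosing covers participants while they are in conditional discontinuation and is silent on the period after restart. Table 4-2 is the schedule given to home users, and no other schedule is set out for trained restarters. The restart tables, as described, do not separate doses by where they were given.

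**Conclusion.** The point holds as an unresolved inconsistency between the on-site observation rule and the home-dosing rule with its schedule. For an already-trained year-1 home user, its firm size is one dose, the second, after a Week 68 or Week 120 restart. After a Week 104 restart the place of doses 2 and 3 is ambiguous. This assumes that Table 4-2 and the Section 6.2.3.1 continuing rule are applied to restarters as written.

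The documents do not show how many participants are affected. The SAP introduction reports early termination for strategic reasons and not because of a safety signal, so few may have reached these restart weeks. That limits the practical reach in this trial. A low-cost correction is still worth making, because the texts disagree on a safety precaution that the protocol itself stresses. The documents do not show that any restart dose was in fact given at home.

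**What to change.** Reconcile Protocol Sections 2.3, 4.1.3, 6.2.3 and 6.2.3.1 with Table 4-2 and its footnote 5, so that one stated rule says where doses 1 to 3 after a restart are given to participants already trained for home dosing. State whether the Week 108 to 116 training visits apply to them. Carry the rule as a footnote to the home-dose rows of Table 4-2, and align home-kit dispensing by the IRT with it. Which rule applies is for the sponsor to decide.

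In the home-administration safety summary (SAP Sections 2.6.1 and 2.6.2), flag any home dose that was among the first three after an interruption. This can still be done after early termination. It would also show whether the Section 6.2.3 requirement was kept.

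The cost is a footnote with aligned wording, an IRT dispensing check and one derived flag. Any change in clinic visits depends on the rule chosen. With the trial stopped, the protocol and IRT changes matter mainly for any remaining conduct or reuse of the design.
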